### 5.1.2 OCS dose titration

At Visit 1, patients will continue with or be switched to prednisone/prednisolone. For patients not previously receiving prednisone/prednisolone as OCS, the conversion table shown in [Appendix F](#) will be used to calculate the equivalent prednisone/prednisolone dose for dose titration.

The OCS dose titration in the reduction phase will be followed as per [Table 2](#) depending on the initial OCS dose and HPA axis evaluation. If [Table 2](#) instructs to reduce dose by 5mg increments, but the initial OCS dose is <5 mg to the nearest dosing level: The 1st reduction would be smaller, rounding down to the nearest 5 mg, then continue on with 5 mg Q2W reductions (examples below):

- e.g. 12.5 → 10 mg → etc.
- e.g. 23 → 20 → 15 → 10 mg → etc.
- e.g. 19 → 15 → 10 mg → etc.

If [Table 2](#) instructs to reduce the initial dose by 2.5mg increments, but the initial dose is <2.5mg to the next dosing level: The 1st reduction would be smaller, rounding down to the nearest 2.5mg, then continue on with 2.5 Q4W reductions (examples below):

- e.g. 8 → 7.5 → 5 → etc.
- e.g. 6.25 → 5 → etc.

For all patients, HPA axis integrity will be evaluated after 4-weeks on 5 mg/day and prior to tapering down the OCS dose (for patients with baseline OCS doses equal to 5 mg/day, this will be assessed 4 weeks after the first dose of benralizumab administration and before initiation of the OCS reduction phase)

First, a screening method with morning serum cortisol is done (8-9 am morning cortisol level), to evaluate whether the patient has:

- Normal cortisol levels
- Complete adrenal insufficiency (AI)

Cortisol levels from the morning cortisol test that are below normal range and above the Complete AI range are considered “Indeterminate,” and require additional testing described below.

Secondly, the ACTH stimulation test (ie, Synacthen®, Cortrosyn™) is done within approximately 1 week in the subset of patients with indeterminate results from the morning cortisol test [see also Section [5.2.1.2](#) for details). The ACTH stimulation test is more specific than the morning cortisol test, and can determine whether the patient has:

- Normal cortisol levels
- Complete AI
- Partial AI.

Investigators may also choose to slow the down-titration to 1 mg Q4W once the patient reaches a OCS dose of 5 mg/day based on patient symptoms alone regardless of cortisol levels. Once there is evidence of recovery, OCS reduction will continue until the patient reaches an OCS dose of 0 mg/day (or lowest OCS dose possible in case no further OCS down-titration is allowed because of the presence of AI as measured by cortisol levels or in case of inadequate asthma control) without losing asthma control.

**Table 2 OCS down-titration approaches**

Initial OCS dose/day	OCS down-titration to reach an OCS dose of:				
	20 mg	10 mg	7.5 mg	5 mg	0 mg
>20 mg	Reduction of 5 mg weekly until reaching dose of 20 mg/day	Reduction of 5 mg Q2W until reaching dose of 10 mg/day	2.5 mg Q2W until reaching dose of 7.5 mg/day	2.5 mg Q4W until reaching dose of 5 mg/day	No AI: reductions of 2.5 mg Q4W until reaching dose of 0 mg/day Risk AI: reductions of 1 mg Q4W and repeat test 2 months later a Complete AI: No OCS dose reduction and repeat test 3 months later b
>10 mg to ≤20 mg		Reduction of 5 mg Q2W until reaching dose of 10 mg/day	2.5 mg Q2W until reaching dose of 7.5 mg/day	2.5 mg Q4W until reaching dose of 5 mg/day	No AI: reductions of 2.5 mg Q4W until reaching dose of 0 mg/day Risk AI: reductions of 1 mg Q4W and repeat test 2 months later a Complete AI: No OCS dose reduction and repeat test 3 months later b
>7.5 mg to ≤10 mg			2.5 mg Q2W until reaching dose of 7.5 mg/day	2.5 mg Q4W until reaching dose of 5 mg/day	No AI: reductions of 2.5 mg Q4W until reaching dose of 0 mg/day Risk AI: reductions of 1 mg Q4W and repeat test 2 months later a Complete AI: No OCS dose reduction and repeat test 3 months later b
>5 mg to ≤7.5 mg				2.5 mg Q4W until reaching dose of 5 mg/day	No AI: reductions of 2.5 mg Q4W until reaching dose of 0 mg/day Risk AI: reductions of 1 mg Q4W and repeat test 2 months later a Complete AI: No OCS dose reduction and repeat test 3 months later b
5 mg					No AI: reductions of 2.5 mg Q4W until reaching dose of 0 mg/day Risk AI: reductions of 1 mg Q4W and repeat test 2 months later a Complete AI: No OCS dose reduction and repeat test 3 months later b

a Risk AI means “partial AI” cortisol testing confirmed with ACTH stimulation testing. After repetition of the test 2 months later, the decision to further reduce OCS dose will be based on the morning cortisol test results. If test results are normal, the OCS dose may be reduced directly to 0 mg/day (if patient is receiving ≤3 mg); the patient will continue receiving 1 mg Q4W if still at risk. If complete AI is indicated, OCS dose will not be modified.

b If morning cortisol test results again indicate complete AI at 3 months, the OCS dose will not be modified as this is the final attempt. If morning cortisol test results indicate risk AI, then reductions will be 1 mg Q4W and, if normal, then reductions will be 2.5 mg Q4W.

**Table 3** “Rescue” OCS down-titration after recovery from an asthma exacerbation or deterioration

Initial OCS dose/day	“Rescue” OCS down-titration after recovery from an asthma exacerbation or deterioration to reach an OCS dose of:		
	10 mg	5 mg	0 mg
>20 mg	Reduction of 5 mg Q4W until reaching a dose of 10 mg/day	Reduction of 2.5 mg Q4W until reaching a dose of 5 mg/day	No AI: Reduction of 2.5 mg Q4W Risk AI: 1 mg/day Q4W and repeat test 2 months later a Complete AI: No OCS dose reduction and repeat test 3 months later b
>10 mg to ≤20 mg	Reduction of 5 mg Q4W until reaching a dose of 10 mg/day	Reduction of 2.5 mg Q4W until reaching a dose of 5 mg/day	No AI: Reduction of 2.5 mg Q4W Risk AI: 1 mg/day Q4W and repeat test 2 months later a Complete AI: No OCS dose reduction and repeat test 3 months later b
>5 mg to ≤10 mg		Reduction of 2.5 mg Q4W until reaching a dose of 5 mg/day	No AI: Reduction of 2.5 mg Q4W Risk AI: 1 mg/day Q4W and repeat test 2 months later a Complete AI: No OCS dose reduction and repeat test 3 months later b
5 mg			No AI: Reduction of 2.5 mg Q4W Risk AI: 1 mg/day Q4W and repeat test 2 months later a Complete AI: No OCS dose reduction and repeat test 3 months later b

a After repetition of the test 2 months later, the decision to further reduce OCS dose will be based on the morning cortisol test results. If test results are normal the OCS dose may be reduced directly to 0 mg/day (if patient was receiving ≤3 mg); the patient will continue receiving 1 mg Q4W if still at risk.

b If morning cortisol test results again indicate complete AI at 3 months, the OCS dose will not be modified as this is the last attempt. If morning cortisol test results indicate risk AI, then reductions will be 1 mg Q4W and, if normal, then reductions will be 2.5mg Q4W.

For prednisone doses below 5 mg, if the exact dose strength is not available in the country, the daily dose to be administered could be achieved by dosing every other day. Daily dose will be the average of 2 days. See Appendix [G](#) for help dosing <5 mg in relation to tablet strength.

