### 5.2.1.1 Morning cortisol test (done at “OCS ≤ 5mg/day [morning cortisol]” visit)

For the morning cortisol test, hold OCS dose and other concomitant medications that could interfere with cortisol results per Section 5.2.1. Serum samples for cortisol will be collected between 8 and 9 am and will be sent to a central laboratory for evaluation. Once the results are available, the site will inform the patient of the results via telephone. Depending on the result, the actions that will be implemented are as follows:

- If cortisol levels are within normal range and the patient does not exhibit any signs and/or symptoms of AI, the patient will continue OCS down-titration by 2.5 mg Q4W

- If cortisol levels are within normal range but the patient exhibits signs and/or symptoms of AI, then OCS down-titration should continue at a slower pace (1 mg Q4W).
- If cortisol levels are below the normal range and above the complete AI range (indeterminate result), then the patient will be instructed to maintain the current OCS dose and come back to the site within 1 week for an ACTH stimulation test (Section 5.2.1.2)
- If complete AI is confirmed, sites will inform patients that the OCS dose will remain the same without further reduction until there is evidence of recovery from the complete AI without worsening of asthma control. The morning cortisol test will be repeated 3 months later, and patients will be educated for symptom awareness of adrenal suppression and use of steroid emergency cards. During this repeat test 3 months later, the patient would also repeat all clinical assessments that were done with the initial morning cortisol test (see Table 1). After the repeat morning cortisol test, the site will inform the patient based on the results as follows:
  - If morning cortisol results at 3 months indicate normal cortisol values, then reductions will be 2.5 mg Q4W, and the patient would subsequently move to maintenance phase at OCS 0mg (or lowest possible dose)
  - If morning cortisol tests at 3 months are indeterminate, then reductions will be delayed further, and the patient would return approximately 1-week later for an ACTH stimulation test:
    - If normal result after ACTH stimulation: Reduce by 2.5mg Q4W then move to maintenance phase at 0mg (or lowest possible dose)
    - If the result is Partial AI after ACTH stimulation: Reduce by 1mg Q4W then move to maintenance phase at 0mg (or lowest possible dose)

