    - If complete AI result after ACTH stimulation: OCS dose will not be reduced further, move to maintenance phase at current OCS dose
  - If morning cortisol tests again indicate complete AI at 3 months, the OCS dose will not be modified as this is the final attempt. The patient would move to maintenance phase at OCS 5mg (or lowest possible dose).

Patients who have Partial AI will undergo an additional morning cortisol test (and if required, ACTH stimulation test for indeterminate result) approximately 1-2 weeks prior to the end of the OCS Reduction phase. Patients who have Complete AI or Partial AI at the end of the OCS Reduction Phase, will undergo a final morning cortisol test (and if required, ACTH stimulation test for indeterminate result) approximately 1-2 weeks prior to the end of the Maintenance phase (prior to EOT). In the absence of evidence of HPA axis recovery, corticosteroid supplementation is recommended during situations of stress (ie, fractures, surgery, trauma, labor, invasive dental procedures, severe systemic infections, major burns, and fever  $>38.5^{\circ}\text{C}$ ). Additionally, patients with Partial AI or Complete AI at the end of the Maintenance phase should be referred to an endocrinologist or other appropriate specialist, per Investigator discretion.

Details related to values for normal, partial AI and complete AI are provided in the laboratory manual.

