  - If morning cortisol test results at 2 months are indeterminate, then reductions will be delayed, and the patient would return approximately 1-week later for an ACTH stimulation test.
    - If normal result after ACTH stimulation: Reduce by 2.5mg Q4W then move to maintenance phase at 0mg (or lowest possible dose)
    - If the result is Partial AI after ACTH stimulation: Reduce by 1mg Q4W then move to maintenance phase at 0mg (or lowest possible dose)

- If complete AI result after ACTH stimulation: OCS dose will not be reduced further, move to maintenance phase at current OCS dose
  - If morning cortisol test results at 2 months indicate complete AI, the OCS dose will not be modified as this is the final attempt. The patient would move to maintenance phase at OCS 5mg (or lowest possible dose).
- If peak cortisol level at 30 minutes indicates complete AI, sites will inform patients that the OCS dose will remain the same without further reduction until there is evidence of recovery from the complete AI without worsening of asthma control. The morning cortisol test will be repeated 3 months later and patients will be educated for symptom awareness of adrenal suppression and use of steroid emergency cards. During this repeat test 3 months later, the patient would also repeat all clinical assessments that were done with the initial morning cortisol test (see [Table 1](#)). After the repeat morning cortisol, the site will inform the patient based on the results as follows:
  - If results indicate normal cortisol values, then reductions will be 2.5 mg Q4W, and the patient would subsequently move to maintenance phase at OCS 0mg (or lowest possible dose)
  - If morning cortisol tests at 3 months indicate indeterminate results, then reductions will be delayed further, and the patient would return approximately 1-week later for an ACTH stimulation test.
    - If normal result after ACTH stimulation: Reduce by 2.5mg Q4W then move to maintenance phase at 0mg (or lowest possible dose)
    - If the result is Partial AI after ACTH stimulation: Reduce by 1mg Q4W then move to maintenance phase at 0mg (or lowest possible dose)
    - If complete AI result after ACTH stimulation: OCS dose will not be reduced further, move to maintenance phase at current OCS dose

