^a Risk AI means “partial AI” cortisol testing confirmed with ACTH stimulation testing. After repetition of the test 2 months later, the decision to further reduce OCS dose will be based on the morning cortisol test results. If test results are normal, the OCS dose may be reduced directly to 0 mg/day (if patient is receiving ≤3 mg); the patient will continue receiving 1 mg Q4W if still at risk. If complete AI is indicated, OCS dose will not be modified.

^b If morning cortisol test results again indicate complete AI at 3 months, the OCS dose will not be modified as this is the final attempt. If morning cortisol test results indicate risk AI, then reductions will be 1 mg Q4W and, if normal, then reductions will be 2.5 mg Q4W.

The **baseline OCS dose** is defined as the dose upon which the patient is stabilised prior to Visit 2 (Week 0). It is calculated as the total OCS dose taken at the first IP dose day.

The **final OCS dose of the OCS reduction phase** will be used to calculate the percentage reduction from baseline. It will be determined by the Investigator and recorded as the final OCS dose of the OCS reduction phase in RAVE (“Asthma Stable Dose”). The final OCS dose will be 0 mg/day or the lowest OCS dose possible in case no further OCS down-titration is allowed because of the presence of AI as measured by cortisol levels or in case of inadequate asthma control. The patient will maintain this dose for at least 4 weeks without worsening of asthma and will initiate the OCS maintenance phase on this OCS dose. If the OCS dose recorded as the final OCS dose in RAVE is not maintained for at least 4 weeks without worsening of asthma, the final OCS dose will be defined as the last stable dose prior. This dose may be the dose at a previous OCS reduction step (e.g. one step higher) or the dose recorded after recovery from an exacerbation, but it will not be a dose recorded during treatment of an exacerbation or AE. The time at which the final OCS dose was reached will be unchanged and time to first increase will be the time from this point until the OCS dose exceeds the defined final dose. The time recorded as the end of the OCS reduction phase will also be unchanged. Similarly, if a patient withdraws during the OCS reduction phase, the final OCS dose will be defined as the last stable dose prior to withdrawal. If no such dose exists, the final dose will be the baseline dose.

The **percentage reduction from baseline** in OCS dose is defined as:

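### The titration-table footnotes can be read to set the taper after a repeat morning cortisol without an ACTH test, whereas Protocol Sections 5.2.1.1 and 5.2.1.2 wait for one; the passages must be reconciled

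*Protocol*

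**What the plan says.** Protocol Section 5.1.2 makes Table 2 the working titration schedule. Table 2 footnote a first defines risk AI as partial AI on "cortisol testing confirmed with ACTH stimulation testing". It then says of the 2-month repeat that "the decision to further reduce OCS dose will be based on the morning cortisol test results". The SAP copy of the table (Section 3.1) carries the same footnote, including: "the patient will continue receiving 1 mg Q4W if still at risk". For the 3-month repeat, footnote b of both tables and of the SAP copy reads: "If morning cortisol test results indicate risk AI, then reductions will be 1 mg Q4W".

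Table 3, used after an exacerbation or deterioration, repeats both footnotes. Its footnote a leaves out the definition of risk AI and the sentence on what happens if complete AI is found.

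Protocol Sections 5.2.1.1 and 5.2.1.2 give a longer procedure for the same repeat tests. At 3 months: "If morning cortisol tests at 3 months are indeterminate, then reductions will be delayed further". At 2 months: "If morning cortisol test results at 2 months are indeterminate, then reductions will be delayed, and the patient would return approximately 1-week later"; that return visit is for ACTH testing. The ACTH result then leads to one of three actions: 2.5 mg Q4W if normal, 1 mg Q4W if partial, and for the third "If complete AI result after ACTH stimulation: OCS dose will not be reduced further, move to maintenance phase at current OCS dose".

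**The concern.** The footnotes name no ACTH step at the repeat test and tie the decision to a morning cortisol. Yet the protocol defines that test as separating only normal, indeterminate and complete AI; partial AI is an ACTH result. A morning cortisol therefore cannot return the class that footnote b asks it to indicate. A site working from the table can reasonably match risk AI to the in-between result and continue at 1 mg Q4W. A site working from Section 5.2.1 waits for the ACTH test.

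If the ACTH test would have shown complete AI, one patient is tapered further and the other goes into maintenance at the current dose. That affects an adrenal safeguard, the final OCS dose from which the primary endpoints are derived, and the AI status reported at the end of the reduction phase.

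**Working it through.** The plan states no figure to reproduce. The check compares the passages and tests whether the disputed case can arise.

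**1. What the footnote can mean.** Protocol Section 5.1.2 calls a morning cortisol between normal and complete AI indeterminate and requires further testing. Footnote b's risk-AI branch therefore has two readings: the reader substitutes indeterminate and tapers on the morning value, or the reader supplies an unstated ACTH step. The footnotes do not say which.

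**2. The paths after an indeterminate repeat.**

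| ACTH result (obtained, or that would be obtained) | Footnotes read literally | Sections 5.2.1.1 and 5.2.1.2 | Agree? |
|---|---|---|---|
| Partial AI | 1 mg Q4W | 1 mg Q4W, after about 1 week's delay | Yes, in rate |
| Normal | 1 mg Q4W | 2.5 mg Q4W | No |
| Complete AI | 1 mg Q4W | No further reduction; maintenance | No |

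**3. Whether the complete-AI case can occur.** From SAP Section 3.3.1, a morning cortisol is indeterminate at 100–350 nmol/L, and ACTH shows complete AI below 250 nmol/L. Let B be the basal value and P the 30-minute value. Assume that P is not below B, and that B at the ACTH visit equals the morning value about a week earlier.

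- Conditions: 100 ≤ B ≤ 350, P < 250, P ≥ B. Together these give 100 ≤ B < 250 nmol/L.
- With oral oestrogen the cut-offs are multiplied by 2 (morning) and 1.5 (ACTH): 2 × 100 = 200 and 1.5 × 250 = 375, giving 200 ≤ B < 375 nmol/L.

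These ranges show where the case is possible. They do not show how often it happens.

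**4. Effect on dose.**

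- Complete AI on ACTH, patient at 3 mg at the 2-month repeat: 3 / 1 = 3 further steps to 0 mg under the literal footnote, none under the sections.
- Normal on ACTH, patient still at 5 mg at the 3-month repeat: 5 / 1 = 5 steps against 5 / 2.5 = 2 steps. The difference is (5 − 2) × 4 = 12 weeks, less about 1 week spent waiting for the ACTH test. Both routes still aim at 0 mg, so this is mainly a difference in time.

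**5. Effect on the primary endpoints (SAP Section 3.1).**

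| Patient whose ACTH would show complete AI | First primary (100% reduction) | Second primary (100%, or ≤5 mg if AI is the reason) |
|---|---|---|
| Tapered to 0 mg, sustained without worsening | Met | Met |
| Held at ≤5 mg, AI the recorded reason, sustained without worsening | Not met | Met |

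In this comparison only the first primary changes.

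**6. Effect on AI reporting.** SAP Section 4.1 takes end-of-reduction status from the repeat test, with or without ACTH, in three classes: normal, partial, complete. An indeterminate repeat with no ACTH result fits none of them. The same section leaves the additional end-of-reduction test out of this status, so that test cannot fill the gap.

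**The case against.** The best defence is that the footnotes are shorthand. Table 2 footnote a defines risk AI as ACTH-confirmed. Carried into footnote b, that definition implies the ACTH step and gives the same outcomes as Section 5.2.1. Other text points the same way: Section 5.1.2 requires more testing after an indeterminate value, Section 5.2.1.2 opens with a general rule to perform ACTH testing in that situation, and the Figure 2 note sends sites to Sections 5.2.1.1 and 5.2.1.2 for repeat testing.

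This harmonising reading is available, and it rules out saying that the footnotes instruct sites to taper on an indeterminate result. They never use that word. But it does not remove the conflict. The sentence after the definition still rests the decision on the morning cortisol. Table 3 has no definition to carry over. The protocol also attaches partial AI to the morning test elsewhere: Table 1 footnote b triggers the ACTH test on it, and the Figure 2 note lists it among the laboratory alerts for either test.

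The protocol also has a backstop, an additional cortisol test shortly before the reduction phase ends for patients with partial AI. It comes after the taper decision in dispute, and it depends on a partial-AI classification that a repeat without ACTH does not supply.

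A reader might infer that the SAP has no place for indeterminate results. That is not so: Section 4.2.7.1 tabulates them at the morning test and follows those patients through later tests. The gap is confined to the three-class status and the shift tables built on it.

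**Conclusion.** This is an internal contradiction in an operative dosing rule, not a design choice. The footnotes define risk AI as ACTH-confirmed and then treat it as something a morning cortisol can indicate; they omit the ACTH step at the repeat test that Sections 5.2.1.1 and 5.2.1.2 require. On a literal reading the paths differ when ACTH would be normal or complete AI. The complete-AI case can change the final OCS dose and the first primary endpoint. Its feasible range of 100 to below 250 nmol/L rests on the two assumptions about basal and 30-minute values stated in the check. The number of patients affected cannot be derived from the documents.

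Three stronger readings are not supported:

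- That every patient with a repeat value of 100–350 nmol/L is affected. Where ACTH shows partial AI, the two texts give the same rate.
- That both primary endpoints move. A patient held at 5 mg or less for AI and a patient sustained at 0 mg both meet the second.
- That a site is deviant whichever page it follows. The remark in SAP Section 2.2.1 on titration below 5 mg is attached to tapering without AI or HPA testing, and no footnote forbids an ACTH test.

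**What to change.** Reconcile footnotes a and b of Protocol Tables 2 and 3, and the SAP copy of Table 2, with Protocol Sections 5.2.1.1 and 5.2.1.2, so that one stated rule covers an indeterminate repeat. Which rule that should be is a clinical decision for the sponsor; this review does not choose it. Stop using risk AI as a morning-cortisol result. Simply putting indeterminate in its place would not be neutral, because it would fix one of the two dosing rules by wording alone.

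In SAP Sections 4.1 and 4.2.7.1, give repeats that were indeterminate with no ACTH result their own row in the normal/partial/complete status and shift tables, and report how many of those patients were tapered further.

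The cost is footnote wording in two protocol tables and one SAP table, plus one row and one count in the AI tables. No new data collection is needed.
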